1 PROTOCOL SUMMARY

1.1 SYNOPSIS

Title:	Designing an Implementation Strategy for Delivering Routine Mental Health Screening and Treatment	
Grant Number:	R34MH125152-01	
Study Description:	This project will develop an implementation strategy for delivering routine mental health screening and treatment to adolescent and young adults with sickle cell disease (SCD). An existing digital cognitive behavioral therapy (CBT) program will be adapted to be engaging and culturally relevant to African Americans. This will be the first study to test a tailored digital CBT for mental health in SCD, and long-term, it will inform the delivery of evidence-based mental health treatment in racial and ethnic minorities living with chronic pain.	
Objectives:	Primary Objective:	Determine whether an adapted digital CBT app will have greater uptake and engagement than standard digital CBT.
	Secondary Objectives:	Determine feasibility of conducting a large scale clinical trial testing digital CBT among adolescents and young adults with SCD.
Endpoints:	Primary Endpoint:	Program Engagement
	Secondary Endpoints:	Pain Interference, Quality of Life
Study Population:	Male and female patients that are between 16 and 35 years of age, have a diagnosis of SCD (any genotype) and report significant depression or anxiety symptoms (i.e., Patient Health Questionnaire [PHQ-9] or Generalized Anxiety Disorder Scale [GAD-7] > 4).	
Phase or Stage:	Phase 1	
Description of Sites/Facilities	
Clinical sites: University of Pittsburgh Medical Center (UPMC),	
Enrolling Participants:	Community-based organizations: Sickle Cell 101, Children's Sickle Cell Foundation	
Description of Study Intervention/Experimental Manipulation:	The study interventions are both cognitive behavioral therapy (CBT) programs delivered through a digital mobile app. The program provides users with brief (5-10 minute) skill building modules and CBT and dialectical behavioral therapy techniques such as relaxation, behavioral activation, distress tolerance, cognitive reframing, and mindfulness meditation, for depression and anxiety. It is for research purposes only. One group will use standard engagement methods while the other group will focus on delivering the CBT in a culturally sensitive manner specific to African Americans.	
Study Duration:	1 Year	
Participant Duration:	1 month	

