1.3 SCHEDULE OF ACTIVITIES

Schedule of interventions and of monitoring patient outcomes		Week of Study			
Outcome	Measure	1	2	3	4
Primary	Engagement: usage days, technique/sessions completed, log-ins, coach contacts				X
	Self-efficacy (SCSES)	X			X
	Mental Health Stigma/ SCD stigma	X			X
Process Evaluation	Perceived relevance and relatability			X	
	Depression (PHQ-9), Anxiety (GAD-7)	X	X	X	X
Quality of Life	Pain interference (PROMIS)	X			X
	Quality of life (ASCQ-Me)	X			X
Medical	Health care utilization: Opioid prescriptions, ED visits, hospitalizations				X

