2.3.3 ASSESSMENT OF POTENTIAL RISKS AND BENEFITS

While enrolled in the study participants will be given access to a health coach. Health coaches are trained personnel in dealing with individuals at risk, and are skilled at working with individuals at risk of feeling anxious or depressed. They will frequently assess participant risk and act accordingly.

Patients are able to stop the digital CBT program at any time, and we will frequently remind patients that they do not have to answer questions if it makes them uncomfortable.

Data Security

Coded data will be stored electronically and saved onto a separate secure database. Once the participant consents, the encrypted data is sent to a RedCap (or similar) secure server. There are two parts to the encrypted data that is transferred from the mobile device to the server: identifiable information upon enrollment and the non-identifiable study data. These two components are stored separately and linked by a unique identifier. The key linking these two are only accessible by the study staff.

This study involves the collection of data over the Internet using mobile devices. Although every reasonable effort will be taken, confidentiality during Internet communication procedures cannot be guaranteed and it is possible that additional information beyond that collected for research purposes may be captured and used by others not associated with this study

Patients will be encouraged to lock their device when not in use and to keep the latest security OS update. Patients will also be encouraged to avoid accessing untrusted sites.

This research is necessary to understand the feasibility of a mobile-technology-based behavioral intervention for mental health that predominantly targets a minority population.

Study endpoints

Primary Outcome Measures

Program engagement. Engagement will be measured by frequency and time on the app, number of lessons completed, and number of interactions (app messages) with health coaches over a 4-week period.

Secondary Outcome Measures

Pain Interference. The PROMIS Pain Interference Scale[86] is a validated questionnaire asking a patient how much day-to-day function is altered by pain. SCD impairs health-related quality of life (HR-QOL) more than most other chronic diseases. PROMIS is designed to allow streamlined, computer-aided administration, and has been tested in multiple populations and conditions including SCD.

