Quality of life and mental health. To assess changes in QOL and emotional distress, participants will complete the following tests at baseline and 1 month: Adult Sickle Cell Quality of Life Measurement Information System (ASCOQ-ME); Emotional Functioning and Social Impact scales;[87, 88] and the Patient Health Questionnaire (PHQ-9),[89, 90] a 9-item measure of depressive symptoms.

Medical Outcomes

In preparation for a large-scale trial, we will pilot the collection of medical outcomes: opioid medication refills, and emergency department visits or hospitalizations for pain crisis. We will collect data retrospectively (from the past 12 months) and prospectively (12 months from date of enrollment) from patient medical records (Table 3). These data will allow us to track health care utilization, as well as lab values (e.g., hemoglobin level) and clinical outcomes (e.g., end-organ damage score).

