8.3.2 ANALYSIS OF THE PRIMARY AND SECONDARY ENDPOINT(S)

Primary and Secondary Analyses. We will employ linear regression models for the primary outcome of usage days and the secondary outcome of techniques and sessions completed (Hypothesis 1) as a function of study arm (standard CBT vs. adapted CBT). We will account for multiple observations for each participant by including a random effect for subject. Additionally, baseline variables with clinically meaningful between-arm differences will be included as covariates.

Process evaluation. Change scores, baseline to 4 weeks, perceived stigma, relevance, relatability, will be tested as potential mediating variables. Contrasts will be estimated to assess the impact of standard and adapted CBT intervention on 4-week differences in perceived relevance, relatability, and stigma. We will then test whether lower perceived mental health

stigma and higher perceived program representativeness and relevance in the adapted CBT arm, mediates any observed group differences in engagement and program satisfaction.

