8.3.9 EXPLORATORY ANALYSES

Due to limited power, evaluation of secondary outcomes will only be exploratory. Linear mixed models will account for change in outcomes over time. Depression (PHQ-9) will be modeled as a function of time, study arm, and time-by-study arm interaction. We will account for multiple

observations for participant by including a random effect for subject. As a secondary investigation, we will test group differences in pain intensity using a similar strategy.

Medical record review will be performed at 12 months post participation. Healthcare utilization will be compared between study arms using generalized linear models to account for count data (i.e., Poisson regression) for each of the following: the number of opioid prescriptions, number of ED visits, and number of hospitalizations over 12 months post study entry. Predictors will include study arm, study site, and baseline depression level. The corresponding health care utilization in 12 months prior to study entry will be entered as a covariate in each model. We will offset each model by participant's time on the study.

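### Section 8.3.9 specifies a test of pain intensity, which no scheduled instrument collects, and gives the declared secondary endpoints (PROMIS Pain Interference, ASCQ-Me) only a generic, unnamed exploratory analysis

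*Combined protocol and SAP*

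**What the plan says.** Section 1.1 lists the secondary endpoints as "Pain Interference, Quality of Life". The study endpoints text within section 2.3.3 gives the instruments. The first is the PROMIS Pain Interference Scale, which "is a validated questionnaire asking a patient how much day-to-day function is altered by pain". For the second it says "To assess changes in QOL and emotional distress, participants will complete the following tests at baseline and 1 month", and it names the ASCQ-Me "Emotional Functioning and Social Impact scales" and PHQ-9. The schedule in section 1.3 has "Pain interference (PROMIS") and ASCQ-Me at weeks 1 and 4 only, and PHQ-9 and GAD-7 every week.

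In the analysis sections, 8.3.2 covers usage days as primary and "the secondary outcome of techniques and sessions completed" under Hypothesis 1. Section 8.3.9 states that secondary outcomes are exploratory because power is limited, and that linear mixed models will handle change over time. It then becomes specific: "Depression (PHQ-9) will be modeled as a function of time", arm and their interaction, with a random subject effect. After that, "we will test group differences in pain intensity using a similar strategy".

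**The concern.** A secondary endpoint should be traceable from its declaration, through its instrument and visit schedule, to a named analysis. Here the chain breaks at the last step for both declared endpoints. In the one place where a pain analysis is specified, the variable is one the trial does not plan to collect. Pain intensity and pain interference are different constructs, and section 2.3.3 itself describes the PROMIS scale in terms of function.

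Two things are at stake. First, analysts would have to decide after the data are in which pain variable, which ASCQ-Me scales, which time points and which contrast to report. Those choices should be fixed beforehand in a pilot meant to inform a larger trial. Second, if the PHQ-9 strategy is carried over to measures taken only twice, a 40-person trial gives up precision that the baseline scores would supply at no cost.

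**Working it through.** **Step 1. Trace each outcome through the document.**

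| Outcome | Declared secondary (1.1, 2.3.3) | Collected (1.3) | Named in 8.3.2 to 8.3.9 |
|---|---|---|---|
| PROMIS Pain Interference | yes | weeks 1 and 4 | no |
| ASCQ-Me quality of life | yes | weeks 1 and 4 | no |
| PHQ-9 | within the quality of life and mental health outcome in 2.3.3 | weekly | yes, model written out |
| Pain intensity | no | no instrument | yes, by reference to the PHQ-9 model |
| Techniques and sessions completed | no; 2.3.3 puts lessons completed within primary engagement | yes, as engagement | yes, called secondary in 8.3.2 |

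The survey descriptions in 4.1, 6.1.2 and 7.3 and the completion definition in 4.4 list no pain-intensity instrument either. The only ASCQ-Me scales named are the two in section 2.3.3, and neither is a pain scale. The numbering of the analysis sections skips 8.3.3, 8.3.7 and 8.3.8, so this check rests on the sections present.

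**Step 2. What the PHQ-9 strategy becomes with two time points.** PROMIS and ASCQ-Me are measured at baseline (week 1) and week 4. With two observations per person and complete pairs, the time-by-arm coefficient in a random-intercept model equals the difference between arms in mean change. Let s² be the outcome variance, taken as equal at both times, and r the correlation between baseline and week 4.

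- Change score: variance = 2s²(1-r)
- Week-4 score adjusted for baseline: variance = s²(1-r²)
- Ratio, adjusted to change: (1-r²)/[2(1-r)] = (1+r)/2
- Saving: 1-(1+r)/2 = (1-r)/2

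The documents give no r, so the values below are assumptions (variances in units of s²).

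| r (assumed) | Change score | Baseline-adjusted | Saving |
|---|---|---|---|
| 0.3 | 1.40 | 0.91 | 35% |
| 0.5 | 1.00 | 0.75 | 25% |
| 0.7 | 0.60 | 0.51 | 15% |
| 0.8 | 0.40 | 0.36 | 10% |

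**Step 3. Context on power.** The plan gives no power figure for these endpoints to reproduce. With 40 randomized and 10% attrition (section 8.1), 40 × 0.90 = 36 remain, or 18 per arm. Assuming a two-sided t-test at alpha 0.05, 80% power needs a standardized difference of about 0.96, and power at 0.5 is about 31%. This agrees with the plan's decision to treat these outcomes as exploratory.

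**The case against.** A reader might infer that the declared secondary endpoints have no analysis at all. The documents do not support that. The opening of 8.3.9 assigns secondary outcomes to an exploratory evaluation by linear mixed models. Section 8.3.6 also refers to analysing secondary outcomes by subgroup, and PHQ-9 has a model of its own. What stands is narrower: the general statement names no outcome, scale, time point or contrast, and the one pain variable named after it is not collected.

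Pain intensity may be a slip for pain interference, since PROMIS Pain Interference is the only pain questionnaire scheduled and section 7.2 gives it priority when a participant discontinues. That is plausible, but the documents do not say so, and the sentence still needs correcting.

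The label in 8.3.2 can be read as the second engagement measure under Hypothesis 1. This is fair: it removes no analysis of pain or quality of life. It does leave unclear which outcomes 8.3.9 means by secondary.

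On precision, the size of the gain depends on an unknown correlation and shrinks as r rises. The formulas take equal variances and treat the regression slope as known. The exact equivalence to a change score needs complete pairs, while the plan allows for 10% attrition. All of this stands, so the full range is shown and the point does not depend on the gain. It is also true that 8.3.2 allows baseline covariates, but only those with meaningful between-arm differences, so it does not commit to adjusting for the baseline score.

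The lack of a GAD-7 model might also look like an omission. GAD-7 is an eligibility route and is collected weekly, but it is not a declared endpoint. Modelling it is optional.

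**Conclusion.** The point holds as an inconsistency in specification. Section 8.3.9 specifies a test of a variable that the trial does not plan to collect, and the two declared secondary endpoints are covered only by a generic exploratory statement. This part rests on comparing sections and needs no assumed figure.

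The precision gain is a supporting argument. It is between 10% and 35% of the variance for assumed correlations from 0.8 down to 0.3, given equal variances and complete pairs. It also takes the week-1 assessment to be the baseline that section 2.3.3 describes.

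The correction should be made, but its reach is limited: these outcomes are already labelled exploratory, and the primary analysis and the sample size are unaffected.

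**What to change.** In 8.3.9:

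- Replace pain intensity with PROMIS Pain Interference.
- Name PROMIS Pain Interference and the ASCQ-Me Emotional Functioning and Social Impact scales as exploratory secondary outcomes.
- For each, regress the week-4 score on arm with the baseline score as covariate, and report the estimated difference with a 95% confidence interval. This takes the place of the time-by-arm random-intercept model for measures taken only twice. The weekly PHQ-9 model can stay as written.

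In 8.3.2 and the synopsis, use one set of labels: either list techniques and sessions completed in the synopsis as a secondary engagement outcome, or change its label in 8.3.2. A GAD-7 model can be added if wanted.

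The cost is SAP wording and three short models on data already scheduled, with no new instrument, visit or participant. If pain intensity was truly intended, an instrument for it would have to be added to the schedule.

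### Low severity: the 12-month utilization counts are planned as plain Poisson regression with no allowance for overdispersion, so their confidence intervals may be too narrow

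*Combined protocol and SAP*

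**What the plan says.** Section 8.3.9 (Exploratory Analyses) models each of three counts over the 12 months after study entry with "generalized linear models to account for count data (i.e., Poisson regression". The abbreviation makes Poisson the named model, not an example of one. On covariates the section says "Predictors will include study arm, study site, and baseline depression level", and then "The corresponding health care utilization in 12 months prior to study entry will be entered as a covariate in each model". On exposure it says "We will offset each model by participant's time on the study".

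The same section limits the weight of the results: "Due to limited power, evaluation of secondary outcomes will only be exploratory". The Medical Outcomes paragraph under section 2.3.3 explains why the data are gathered: "In preparation for a large-scale trial, we will pilot the collection of medical outcomes". It sets the prospective window as "prospectively (12 months from date of enrollment) from patient medical records". The Synopsis (section 1.1) gives the secondary objective: "Determine feasibility of conducting a large scale clinical trial testing digital CBT among adolescents and young adults with SCD".

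No section mentions overdispersion, a scale parameter, robust standard errors or negative binomial regression. The subject random effect in section 8.3.9 belongs to the linear mixed model for PHQ-9, and by extension to the pain analysis. It is not stated for the counts, which supply one post-entry total per participant.

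**The concern.** A Poisson model has no free variance parameter: given the covariates, variance equals mean. The offset deals with unequal exposure time. The prior-year count absorbs part of the stable difference between patients. Neither estimates variance left over after adjustment.

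There is some reason to expect such variance. Section 5.1 admits any SCD genotype, and section 5.5 recruits from pediatric clinics, adult clinics and community organizations. If it is present, standard errors are too small, and intervals labelled 95% cover less often than that.

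What is at stake is the stated precision of three pilot rate ratios. There is a possible knock-on effect: these outcomes are piloted for a larger trial, and the sample size for a count endpoint is proportional to the dispersion. A plain Poisson analysis does not report that quantity.

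**Working it through.** **No plan figure to reproduce.** The documents give no event rate, variance, alpha or power for the utilization analysis.

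**Inputs from the documents.** 40 participants (section 8.1), allocated 1:1 (section 6.3), so 20 per arm. Predictors are arm, site, baseline depression and prior 12-month count (section 8.3.9). Attrition is 10% at 4 weeks (section 8.1).

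**Assumed inputs.** Mean 2 or 4 events a year; no true arm effect; site coded as binary; gamma-Poisson counts with variance/mean of 1, 1.5, 2, 3 or 5 before covariates; 50%, 80% or 100% of patient frailty shared between the prior and follow-up years.

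**Step 1, closed form.** If residual variance is φ × mean, the true standard error is √φ times the Poisson one, and a nominal 95% interval covers with probability 2Φ(1.96/√φ) − 1.

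| Residual φ | SE ratio √φ | Actual coverage | Two-sided type I error |
|---|---|---|---|
| 1 | 1.00 | 95.0% | 5.0% |
| 1.5 | 1.22 | 89.0% | 11.0% |
| 2 | 1.41 | 83.4% | 16.6% |
| 3 | 1.73 | 74.2% | 25.8% |
| 5 | 2.24 | 61.9% | 38.1% |

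An arm-only simulation (20 per arm, 20,000 runs per setting) agrees: coverage was 89.1-89.5%, 83.6-84.0%, 74.2-74.4% and 62.1-63.2% at φ = 1.5, 2, 3 and 5.

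**Step 2, with the planned covariates.** Here φ is what remains after adjustment, so it is smaller than the starting variance/mean. The model was a Poisson GLM on arm, site, baseline depression and raw prior count, with 5,000 trials per setting. Five coefficients leave 40 − 5 = 35 df. Rejection rates at nominal 5% are shown with 50% shared frailty first and 100% second.

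| Variance/mean before covariates | Mean | Plain Poisson, % | Pearson-scaled, t (35 df), % | HC3-type robust, t, % |
|---|---|---|---|---|
| 1 | 2 | 4.7 | 4.7 | 3.6 |
| 1 | 4 | 5.0 | 5.1 | 4.1 |
| 1.5 | 2 | 10.6 / 8.2 | 5.4 / 4.9 | 3.7 / 3.8 |
| 1.5 | 4 | 10.1 / 9.1 | 4.8 / 5.1 | 3.4 / 3.7 |
| 3 | 2 | 21.4 / 14.1 | 5.6 / 5.6 | 3.9 / 3.5 |
| 3 | 4 | 22.4 / 14.4 | 5.0 / 5.6 | 4.0 / 3.9 |
| 5 | 2 | 33.2 / 21.1 | 6.4 / 7.9 | 4.2 / 3.3 |
| 5 | 4 | 34.8 / 20.8 | 6.1 / 7.2 | 4.2 / 3.8 |

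At variance/mean 2, plain Poisson rejects 11-15%. Median residual dispersion (Pearson chi-square/df) ran from 1.28 to 3.60 across the overdispersed settings. The mean log rate ratio stayed within 0.01 of zero, so the point estimates are not at fault.

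**Step 3, sensitivity.** With 18 per arm (20 × 0.9), plain Poisson rejects 9-33% and the scaled version 5-8%. With log(prior + 1) in place of the raw prior count (2,500 trials per setting), the figures are 9-34% and 5-7%. A separate covariate-adjusted run of 3,000 trials per setting gave 8.7-34.1% and 4.9-8.8%.

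**Step 4, what the dispersion would inform.** For illustration, assume a future trial with mean 2 a year, rate ratio 0.75 (so 1.5 in the other arm), 80% power and two-sided 5%:

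n per arm = (1.96 + 0.8416)² × φ × (1/2 + 1/1.5) / (ln 0.75)² = 110.7 × φ.

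Rounded up, this gives 111 at φ = 1.0, 144 at 1.3, 222 at 2.0 and 399 at 3.6. An estimate from 40 people is imprecise: where its median is 2.3, the 10th to 90th percentiles are 1.6 to 3.4.

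**The case against.** The strongest reply is that little depends on this. Section 8.3.9 calls the analysis exploratory and sets no alpha or decision rule, and section 2.3.3 pilots the collection of the data. That stands, and it is why the severity is low.

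Second, the section is silent on the variance estimator, and Poisson regression with scaled or robust standard errors is still Poisson regression. That is fair: the remedy keeps the model and the point estimates. But with no estimator stated, the default is the model-based one.

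Third, the evidence for overdispersion is thin, and the plan already adjusts for each patient's own prior-year count. That adjustment helps. With frailty fully shared between years, rejection at variance/mean 5 falls from about 33-35% to about 21%. It does not remove the problem: even then the rate is 8-9% at variance/mean 1.5. The 35% figure needs both variance/mean 5 and only half-shared frailty.

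Fourth, no document says the larger trial will have a count endpoint, and dispersion can be computed later from the raw counts. Both are true, so the sample-size argument is only a secondary benefit.

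Finally, Pearson scaling is imperfect, with up to 7.9% rejection in the main run, where the robust version gives 3-4%. Either is much closer to nominal than the plain model.

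**Conclusion.** The concern holds as a conditional statement. Section 8.3.9 specifies Poisson regression for three counts without any dispersion allowance. If the counts are overdispersed given the covariates, the intervals are too narrow. Under the assumed settings (mean 2 or 4 events a year, variance/mean 1.5 to 5 before covariates, half to full sharing of frailty), the actual error rate at nominal 5% is 8% to 35%. If the counts are truly Poisson, nothing is wrong. The documents cannot show which case applies.

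The rate ratios, the primary endpoint and the trial's sample size are unaffected, and no planned conclusion changes. This is an optional improvement. Fixing the method in advance also avoids choosing the variance estimator after seeing the results.

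**What to change.** Replace the model sentence in section 8.3.9 with something like:

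> Each count will be analysed by Poisson regression with the planned covariates. Standard errors will be scaled by Pearson chi-square/df, with t-based 95% confidence intervals. Rate ratios, their intervals and the estimated dispersion will be reported. The offset will be the log of medical-record follow-up time within 12 months of study entry.

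Small-sample robust (HC3-type) standard errors would serve equally well. Negative binomial regression is possible but less dependable at this size: in simulation it gave no usable standard error in about 29% of truly Poisson data sets and 0-12% of overdispersed ones.

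The last sentence only clarifies. Time on the study is undefined, and the Synopsis gives a participant duration of one month while these outcomes run for 12. The natural reading, follow-up within the 12-month window, is harmless.

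**Cost.** SAP wording and one software option. If the counts are truly Poisson, the t reference widens intervals by 3.6% (2.030/1.960 = 1.036); the simulated median net widening is 2-3%. With overdispersion, median widths grow 1.17 to 1.97 times, which is the precision the plain model leaves out. The offset already requires a time for each participant, although record follow-up may be harder to establish for people recruited through community organizations (section 5.5).

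A separate wording point in the same section: it refers to pain intensity, whereas the Synopsis, the Schedule of Activities and section 2.3.3 list pain interference (PROMIS in the latter two). These should be reconciled.

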8 STATISTICAL CONSIDERATIONS

8.1 SAMPLE SIZE DETERMINATION

We anticipate randomizing, in an equal allocation ratio, a total of 40 participants with follow-up through at least 4 weeks, which will be the main time point for primary analysis.

For the primary test of engagement comparing standard vs. adapted digital CBT, the power calculation is based on the comparison of intervention groups for the main outcome of difference in usage days modules completed. Based on prior data (see preliminary data - Digital CBT in Medical Clinics), we would expect 50% less engagement for African Americans vs whites with our standard digital CBT app. Thus, to detect a 150% improvement in engagement related to adapted vs standard CBT for usage days (e.g 20 vs 10 usage days), with 80% power, a total of N=34 (n=17 per arm) is necessary. We are accounting for 10% attrition at 4 weeks.

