8.3 STATISTICAL ANALYSES

8.3.1 GENERAL APPROACH

All primary and secondary analyses will be preceded by descriptive analyses of baseline and clinical characteristics. Summary statistics will include means and standard deviations for continuous variables, and sample proportions for categorical variables. Median and interquartile range values will accompany continuous variables that are non-normal. Results will be presented for the entire sample and stratified by intervention arm. We will assess between-arm imbalance of baseline covariates by calculating standardized mean differences. For continuous variables, we will assess normality by visually inspecting univariate distribution via a normal probability plot. Transformations will be implemented if required.

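### Section 8.3.9 leaves open the form of the prior-year count and any overdispersion method in its Poisson utilisation models; literal use can lose precision and gives standard errors that are too small

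*Combined protocol and SAP*

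**What the plan says.** Section 8.3.9 (Exploratory Analyses) states: "Healthcare utilization will be compared between study arms using generalized linear models to account for count data (i.e., Poisson regression"). The outcomes are "the number of opioid prescriptions, number of ED visits, and number of hospitalizations over 12 months post study entry". The model terms are given as "Predictors will include study arm, study site, and baseline depression level", followed by "The corresponding health care utilization in 12 months prior to study entry will be entered as a covariate in each model" and "We will offset each model by participant's time on the study". The link function is not named, but a time offset makes sense only on the log scale.

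The section does not say whether the prior-year count enters raw, logged or in categories. It names no overdispersion method and no influence check.

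Two other statements bear on the point. Section 8.3.1, after a normality check by probability plot for continuous variables, adds "Transformations will be implemented if required". Section 8.3.9 also limits the weight of these analyses: "Due to limited power, evaluation of secondary outcomes will only be exploratory". Section 8.1 gives the size, "a total of 40 participants with follow-up through at least 4 weeks".

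**The concern.** Two separate gaps meet in one model.

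- **Form of the covariate.** Under a log link, a raw count with slope b multiplies the expected rate by exp(b) for every extra event in the previous year. The covariate and the outcome are the same kind of event counted over 12-month windows. A natural working model is that next year's rate is roughly proportional to last year's, which is linear in the log of the prior count. If so, the raw term misfits high users, and the arm rate ratio is estimated less precisely than it could be.
- **Error model.** Plain Poisson regression sets the variance equal to the mean. If patients differ in their underlying rate beyond what the covariates capture, the variance exceeds the mean and the nominal standard errors are too small.

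At stake are the precision and the error rate of three exploratory comparisons. The study-endpoints section says the medical outcomes are piloted to prepare for a larger trial, so both the estimates and the model may be carried forward.

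**Working it through.** **1. The plan's own figure.** No power, precision or event rate is given for utilisation, so there is nothing to reproduce. The only sizing figure is 34 participants (17 per arm) for usage days; 34/(1 - 0.10) = 38, against 40 planned. It has no bearing on these models beyond fixing N.

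**2. Inputs.** From the documents: N=40, 1:1 allocation, and a Poisson model with arm, site, baseline depression, prior-year count and offset. Assumed, because the documents give no values: mean yearly count 1.5, 3 or 10; gamma between-patient heterogeneity with shape k = 0.5, 1 or 2 (smaller k means more skew); equal exposure; no true arm effect. Each setting was simulated 500-600 times.

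**3. What the form implies.** For illustration, take a raw slope of 0.1 per event. Moving from 20 to 40 prior events multiplies the predicted rate by exp(0.1 × 20) = 7.4. With log(1+count) and slope 1, the same move multiplies it by 41/21 = 1.95.

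Under the assumed gamma model with stable patient rates and mean m, the expected next-year count given prior count x is m(k + x)/(k + m). Its log is log(k + x) plus a constant. At k = 1 this is exactly log(1 + x) with slope 1.

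**4. Precision: variance of the arm log rate ratio, raw divided by log(1+count), N=40.**

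| Assumed truth | Setting | SD raw | SD log | Variance ratio |
|---|---|---|---|---|
| Stable patient rate | mean 3, k=1 | 0.295 | 0.272 | (0.295/0.272)² = 1.18 |
| Stable patient rate | mean 10, k=0.5 | 0.306 | 0.168 | (0.306/0.168)² = 3.3 |
| Rate drifts between years | mean 3, k=2 | 0.349 | 0.342 | 1.04 |
| Rate drifts between years | mean 10, k=0.5 | 0.457 | 0.373 | 1.50 |
| Log rate linear in raw count | mean 3, k=1 | 0.268 | 0.301 | 0.79 |
| Log rate linear in raw count | mean 10, k=0.5 | 0.223 | 0.306 | 0.53 |

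Over all settings the ratio is 1.06-3.4 with stable rates, 1.02-1.50 with drifting rates, and 0.53-0.96 when the log rate is linear in the raw count. A second simulation under stable and drifting rates gave 1.03-2.7.

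**5. Influence of high users, N=40.** The top 3 of 40 patients carry about 40-49% of the information on the covariate slope with raw coding and 27-36% with log coding. Their share of total leverage hardly differs: 22-32% raw, 19-29% log.

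**6. Nominal Poisson errors.** With stable rates and the correct covariate form, the variance-to-mean ratio given x is 1 + m/(k + m), which always lies between 1 and 2. At m=3, k=1 it is 1.75, and the false-positive rate is about 2[1 - Φ(1.96/√1.75)] = 14%. At m=1.5, k=2 it is 1.43, giving 10%. Simulation with log coding and stable rates gave 9-18%, in agreement.

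With drifting rates the gap is wider. The ratio of empirical SD to mean model SE predicts the rejection rate:

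| Setting | Coding | SD / model SE | Predicted | Simulated |
|---|---|---|---|---|
| mean 3, k=1 | raw | 0.433/0.209 = 2.07 | 34% | 32% |
| mean 3, k=1 | log | 0.402/0.205 = 1.96 | 32% | 32% |
| mean 10, k=0.5 | raw | 0.457/0.123 = 3.72 | 60% | 58% |
| mean 10, k=0.5 | log | 0.373/0.119 = 3.13 | 53% | 55% |

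Overall, false-positive rates are 10-42% raw and 9-18% log with stable rates, and 17-58% raw and 17-55% log with drifting rates. Uncorrected sandwich errors brought them down to roughly 6-16%. That is much better but still above 5%, which is why a small-sample correction is needed.

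**The case against.** A reader might infer that the plan enters the count untransformed and that a few heavy users then dominate the fit. The documents do not support this. Section 8.3.9 is silent on form, and Section 8.3.1 allows transformation. The total leverage of the top users is nearly the same under either coding. The extra concentration is in the covariate slope, which is a nuisance term.

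A reader might also take the loss of precision as established. It is conditional: no event rate, spread or year-to-year correlation is documented, the loss can be as small as 2%, and it reverses if the log rate is linear in the raw count. In every setting tested at N=40, raw adjustment was still better than none: the unadjusted variance was 1.08-2.5 times the raw-adjusted variance. The analysis is exploratory, and no stated decision rests on it.

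All of this stands as a limit on the point, but it does not remove it. The Section 8.3.1 rule concerns normality of continuous variables, which is not the criterion for a covariate in a Poisson model, and it leaves the choice until the data are seen. The possible reversal is itself a reason to fix the form beforehand. The overdispersion problem does not depend on the coding: it appears with both.

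**Conclusion.** The point holds as a gap in specification with two consequences of different strength.

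The firmer one is the error model. With any appreciable between-patient heterogeneity, nominal Poisson errors are too small; at N=40 the simulated false-positive rate with the raw count is roughly 10-58% against 5%, and changing the covariate's form does not by itself repair it.

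The weaker one is precision. If yearly rates are roughly proportional within a patient, literal use of the raw count costs about 2% to more than 100% in the variance of the arm log rate ratio. If the log rate is linear in the raw count, log coding is the worse choice. Proportionality is the more natural assumption for the same event counted in successive years, but the documents cannot confirm it.

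The sizes rest on assumed means, gamma heterogeneity and equal exposure. The consequences are confined to the exploratory utilisation comparisons; the primary engagement endpoint is unaffected. This is a minor, worthwhile improvement.

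**What to change.** In Section 8.3.9, state that log(1 + prior-12-month count) is the covariate in each utilisation model. State also that standard errors are overdispersion-robust (sandwich or quasi-Poisson) with a small-sample correction, because N=40. A short check of the arm estimate with the highest users left out would show how far it depends on them.

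The cost is a sentence or two in the plan. It needs no new data and no change in sample size. Confidence intervals for the utilisation rate ratios will be wider than nominal Poisson intervals, which is the intended correction.
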